## 15 STUDY ADMINISTRATION

### 15.1 STUDY LEADERSHIP

In addition to the clinical centers, the trial is implemented through a Clinical Coordinating Center (CCC) at Cleveland Clinic; a Data Coordinating Center (DCC) located in Research Triangle Park, NC at RTI International; and various collaborators providing specific expertise as described below and depicted in Figure 4.

**Figure 4.** Organizational Structure of the Pomalidomide for the Treatment of Bleeding in Hereditary Hemorrhagic Telangiectasia Study

The National Heart, Lung, and Blood Institute (NHLBI) will serve as study sponsor. The Steering Committee will consist of NHLBI representatives, and a subset of site investigators who provided input to the design of the study as part of the NHLBI U34 Planning Grant. This leadership team will be responsible for all major scientific and operational decisions. Other trial committees will report to the Steering Committee at regular monthly meetings held by teleconference (or in person if necessary).

**Cure HHT**, directed by [name], is a critical component of the overall structure of this trial. The HTTFI maintains a database of more than 10,000 HHT patients, many of whom are not followed at HHT Centers of Excellence and thus do not overlap with the rosters maintained by sites participating in this study. Cure HHT will serve as the primary marketing and information distribution tool for this study, and will work closely with the PI to develop materials for dissemination to patients with HHT, and to physicians who treat HHT patients.

The **Data Safety Monitoring Board** (DSMB) will consist of approximately seven members and be directly appointed by NHLBI following recommendations of qualified individuals by the PI. Individuals on the DSMB will be familiar with the conduct of clinical trials, and have expertise in the management of HHT. The role of the DSMB will be as follows:

- To meet biannually by teleconference with the CCC and DCC PIs who will update trial progress.
- As a component of this teleconference, the DSMB will hold a closed-door discussion of progress, with specific focus on all AEs, as well as any SAEs that may have occurred.
- Following review and discussion of this data, the DSMB will determine whether any potential safety issues exist that would preclude the trial from continuing, or that need to be addressed.
- The DSMB will provide their recommendations (including continuation/discontinuation of the trial) to the NHLBI Director.
- The DCC will be responsible for documenting the proceedings of the DSMB meetings, and obtaining the signature of the designated DSMB chair.

[name] will serve as the **Independent Medical Monitor** (IMM) for this study. His role will be as follows:

- To review all AEs that occur during the trial. In particular, he will review all SAEs within 24 hours of their occurrence.
- To prepare regular reports concerning SAEs and submit to the CCC PI, and subsequently to the DSMB and, as appropriate, to FDA as required by the IND.
- Like the DSMB, decisions of the IMM will be made independently of the PI, and he will have the authority to recommend that the trial be placed on hold if he observes an SAE that s/he considers trial-related that is of sufficient severity to threaten patient safety.
- The IMM may participate in DSMB reviews if he wishes, though this will not be compulsory, and in some cases he may wish to seek consultation from the DSMB.
- In situations in which the trial is put on hold or terminated, the IMM will communicate this directly to the PI and DCC, as well as to NHLBI.

- If the IMM is unavailable for an extended period of time (i.e., extended vacation, sabbatical, illness) a backup IMM will be nominated by the CCC PI and approved by the NHLBI Program Official.

The **Quality Control (QC) Committee** will include experts from the DCC and CCC. Involvement of clinical center PIs is optional. The roles of the QC committee will be as follows:

- Establish and oversee the development, implementation and monitoring of the essential trial quality control processes, including both informatics QC and clinical site QC.
- Review regular QC reports and work with the Steering Committee and Operations and Recruitment Committee to assure trial quality.
- Provide reports on overall trial quality to the Steering Committee on a semiannual basis.
- Provide reports on overall trial quality to the PIs for inclusion in annual NIH progress reports.

## 16 CONFLICT OF INTEREST POLICY

All investigators will be expected to comply with institution-specific conflict of interest procedures that could potentially impact this trial. When these occur, they may most commonly be addressed by full disclosure. If this is felt to be insufficient, then the investigator will be replaced.

### HHT-SPECIFIC QOL QUESTIONNAIRE

1. How often in the past 4 weeks has an activity for your work, school, or regularly scheduled commitments been ***interrupted by a nose bleed?***

0=Never

1=Rarely

2=Sometimes

3=Often

4=Always

2. How often in the past 4 weeks has an activity with your partner, family, or friends been ***interrupted by a nose bleed?***

0=Never

1=Rarely

2=Sometimes

3=Often

4=Always

3. How often in the past 4 weeks have you ***avoided social activities*** because you were ***worried about having a nose bleed?***

0=Never

1=Rarely

2=Sometimes

3=Often

4=Always

4. How often in the past 4 weeks have you had to miss your work, school, or regularly scheduled commitments because of ***HHT-related problems other than nosebleeds?***

0=Never

1=Rarely

2=Sometimes

3=Often

4=Always

**Scoring:**

A total score is calculated by summing the items (each scored from 0-4). The total score ranges from 0 (no limitations) to 16 (severe limitations). If any items are not answered, the total score will not be calculated.

15	APPENDIX 1 EPISTAXIS SEVERITY SCORE SCORING	30
16	APPENDIX 2 SCREEN SHOT OF EPISTAXIS DIARY	32
17	APPENDIX 2 INTERIM ANALYSIS AT 50%	33
18	APPENDIX 3 INTERIM ANALYSIS AT 75%	35

LIST OF ABBREVIATIONS

Abbreviation:	Deciphered:
AE	Adverse Event
AVM	arteriovenous malformations
CRF	Case Report Form
CI	Confidence interval
CTCAE	Common Terminology Criteria for Adverse Events
DSMB	Data Safety and Monitoring Board
EOS	End of study visit, scheduled to be 4-weeks post-treatment
ESS	Epistaxis Severity Score
HCT	Hematocrit
HHT	Hereditary Hemorrhagic Telangiectasia
MedDRA	Medical Dictionary for Regulatory Activities
Neuro-QoL	Quality of Life in Neurological Disorders
NHLBI	National Heart, Lung, and Blood Institute
NIH	National Institutes of Health
PI	Principal Investigator
PROMIS	Patient Reported Outcomes Measurement Information System
QOL	Quality of Life
REMS	FDA mandated Risk Evaluation and Mitigation Strategy
SAE	Serious Adverse Event
SAS	Statistical Analysis System

1 BACKGROUND

This study will address the efficacy of pomalidomide in the treatment of epistaxis in patients with Hereditary Hemorrhagic Telangiectasia (HHT) who have anemia and/or require blood transfusion or iron infusion for treatment of bleeding-induced anemia and iron deficiency. HHT is an inherited disease clinically diagnosed using the Curacao criteria, which consists of 1) spontaneous and recurrent epistaxis, 2) telangiectasias at characteristic sites, 3) visceral arteriovenous malformations (AVMs) or telangiectasias, and 4) a first degree relative with HHT (inheritance is usually autosomal dominant). Patients with three criteria are considered to have definite HHT, and those with 2 criteria probable HHT, while one or no criteria make the diagnosis unlikely. Patients eligible for this study will have a diagnosis of definite or probable HHT. Estimates suggest that HHT affects between 1 in 1,330 and 1 in 10,000 individuals. Since many physicians are not familiar with the disease, only 10% of patients with HHT may actually be diagnosed. Significant manifestations of HHT often do not appear until the third or fourth decades, sometimes later.

There are no evidence-based guidelines for managing HHT, and there is no medical therapy universally accepted as efficacious; thus, treatment is not standardized. Historically, interventional procedures have formed the mainstay of HHT therapy. However, though often effective initially, such procedures are associated with a high incidence of recurrent bleeding from new AVMs or AVMs not visualized during endoscopic procedures. Epistaxis is the most common clinical manifestation of HHT, affecting $\geq 80\%$ of patients, and leading to significant impairment in quality of life. There exists very little information concerning the effect of therapy on QOL in patients with HHT. To assess the effect of pomalidomide on QOL in HHT patients, we will administer QOL assessments before, during and after therapy.

2 PURPOSE OF THE ANALYSIS

This statistical analysis plan (SAP) contains detailed information about statistical analysis to be performed to assess the efficacy and safety of pomalidomide as a treatment for reducing the severity of epistaxis.

3 STUDY OBJECTIVES AND OUTCOMES

3.1 Study Objectives

3.1.1 Primary Objectives

1. To determine efficacy of pomalidomide compared to placebo for the reduction in severity of epistaxis after 24 weeks of treatment.

3.1.2 Secondary Objectives

1. To determine the safety and tolerability of pomalidomide for the treatment of HHT.
2. To determine if pomalidomide treatment improves quality of life in HHT.
3. To determine whether a continued response to pomalidomide is evident 4 weeks after treatment discontinuation.
4. To develop a biorepository for future studies to define biomarkers predictive of pomalidomide response and allow investigations into the biology of HHT and mechanisms of pomalidomide.

3.2 Outcomes

3.2.1 Primary Outcomes

The primary endpoint of this study is change of the Epistaxis Severity Score from baseline to week 24 in the placebo and pomalidomide-treated groups. The ESS at baseline and each follow-up visit will reflect the patient's symptoms and bleeding over the previous 4 weeks.

3.2.2 Key Secondary Outcomes

1. Amount of parenteral iron administered (in mg) during the 24-week treatment period in the pomalidomide and placebo groups (calculated as average mg/4-week interval to account for patients who discontinue early).
2. Amount of packed red blood cell transfusions (in units) during the 24-week treatment period in the pomalidomide and placebo groups (calculated as average units/4-week interval to account for patients who discontinue early).
3. Change in Neuro-QoL™ Satisfaction with Social Roles and Activities Short Form (V1.1) T-score from baseline (randomization visit) to weeks 12 and 24 (key timepoint), and the 4-week post-treatment follow-up visit in the pomalidomide and placebo groups.
4. Change in the HHT-specific QOL total score from baseline to weeks 12 and 24 (key timepoint), and the 4-week post-treatment follow-up visit in the pomalidomide and placebo groups.
5. Change in average daily epistaxis duration from the four-week screening period prior to baseline to weeks 8-12 and to weeks 20-24 (key timepoint), and to weeks 1-4 post-treatment in the pomalidomide and placebo groups.

3.2.3 Other Secondary Outcomes

1. Change in PROMIS® Emotional Distress-Depression Short Form (V1.0) T-score from baseline (randomization visit) to weeks 12 and 24 (key timepoint), and the 4-week post-treatment follow-up visit in the pomalidomide and placebo groups.
2. Change in PROMIS® Fatigue Short Form (V1.0) T-score from baseline (randomization visit) to weeks 12 and 24 (key timepoint), and the 4-week post-treatment follow-up visit in the pomalidomide and placebo groups.
3. Proportion of patients requiring no red blood cell transfusion or parenteral iron infusion during the 24-week treatment period in the pomalidomide and placebo groups.
4. Change in the ESS from baseline to that recorded at each individual patient assessment, including the 4-week post-treatment follow-up visit.
5. Change in the ESS from baseline to the average of the week 16, 20 and 24 assessments.
6. Proportion of patients requiring endoscopic interventions for management of bleeding during the 24-week treatment period in the pomalidomide and placebo groups.
7. Incidence and severity of adverse events in the pomalidomide and placebo groups including but not limited to:
 - Venous thromboembolism
 - Arterial thromboembolism
 - Thrombocytopenia
 - Neutropenia
 - Peripheral neuropathy
 - Fatigue
 - Constipation/diarrhea
 - Rash

- Any other AEs or SAEs of at least moderate severity that are possibly related to pomalidomide and deemed medically relevant at masked data review.

8. Change in iron/hemoglobin-related studies including iron saturation, ferritin, hemoglobin, hematocrit, MCV, and MCHC.

3.2.4 Exploratory Outcomes

1. Rate of relapse at the 4-week post-treatment follow-up visit, where relapse is defined as a return of the ESS to the baseline value or greater in pomalidomide (or placebo)-treated subjects.
2. Median time after initiation of pomalidomide to obtain a decrease in the ESS of at least 1.0 in the in pomalidomide-treated subjects compared to placebo.
3. Effect of genotype on the response to pomalidomide.

Outcome Modification History:

The protocol originally specified that the PROMIS® Satisfaction with Social Roles and Activities Short Form 8a (V2.0) was to be the 3rd key secondary outcome. Part-way through the study (summer 2022) it was determined that due to an inadvertent error, the CRF meant to collect the PROMIS instrument instead corresponded to the Neuro-QoL™ Short form V 1.1 instrument with the same name, number of items, and response categories, but different items. As the study was over 50% enrolled when this issue was identified, the decision was made to update the protocol to specify the Neuro-QoL instrument instead of the PROMIS instrument. This update was made in Protocol version 2.10.

Although developed as part of an assessment system for people with neurological conditions, the NeuroQoL Satisfaction with Social Roles and Activities is scored relative to a general population sample (Gershon et al 2012), supporting its use in non-neurologic health conditions. For both the PROMIS and Neuro-QoL instruments, a T-score of 50 represents the average for the United States general population with a standard deviation of 10, and calibration testing was performed on a large sample of the general population. PROMIS was developed in 2016. Neuro-QoL was developed in 2014, and the T-score calculations are based on a normative population of over 5,000 individuals. The protocol was initially designed with a 12-week follow-up period, which was modified to a 4-week period in Protocol version 2.8 (August 2, 2021). Prior to the change, 20 participants had completed the 12-week rather than 4-week follow-up.

Additionally, protocol update version 2.8 (8/2/2021) clarified that the early termination visit available in the EDC system was to be used only for participants who withdrew consent and did not agree to complete the 4-week post-treatment follow-up. Prior to the amendment, there were a number of subjects with an early termination (ET) visit which should have been recorded as a regular study visit or a 4 week (or 12 weeks) post-treatment visit. These cases were manually reviewed, and the ET visits will be re-classified in all reporting and statistical analysis to be either a C1-C6 treatment visit, or an end-of-study (EOS) visit. If the number of days since the prior visit and prior study drug dispensing was within 28 days, it was recoded to the next cycle visit. If the number of days since the prior visit or the prior study drug dispensing was > 28 days, then it was recoded as an EOS visit. Details are documented in the analysis file specification document.

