## 7.3.7 TABLE 4: SCHEDULE OF EVENTS TABLE

Visit	Screen and Baseline		Treatment Period						End of Study	
	SC	BL	C1	C2	C3	C4	C5	C6	EOS	ET 
Study Procedures	Week -4 to -8 	Week 0	Week 4 0-5 Days*	Week 8 0-5 Days*	Week 12 0-5 Days*	Week 16 0-5 Days*	Week 20 0-5 Days*	Week 24 0-5 Days	Week 28 (4 week follow up) 0-7 Days	Only for withdrawn consent
Informed Consent	X									
Enrollment Criteria	X									
Demographics	X									
Medical History	X									
Concomitant Medications	X	X	X	X	X	X	X	X	X	X
Physical Exam	X	X 1*	X 	X 	X	X 	X 	X	X	X
Vital Signs 	X	X	X	X	X	X	X	X	X	X
Genetic Testing 		X								
Iron Infusion	X 	X	X	X	X	X	X	X	X	X
Blood Transfusion	X 	X	X	X	X	X	X	X	X	X
Adverse Events		X	X	X	X	X	X	X	X	X
ESS	X 	X	X	X	X	X	X	X	X	X
Epistaxis Duration Diary	X	X 		X	X 		X	X 	X 	X 
CBC with differential	X	X	X	X	X	X	X	X	X	X
CMP	X	X	X	X	X	X	X	X		X
Iron Studies 	X	X	X	X	X	X	X	X	X	X
INR and aPTT (or PTT per local lab designation)	X									
Biorepository Collection	X	X 			X 			X 	X	X 
QOL  surveys		X			X			X	X	X
Pregnancy Testing 	X	X	X	X	X	X	X	X		X 
Randomization		X								
Drug Dispensation		X	X	X	X	X	X			
Drug Return			X 	X 	X 	X 	X 	X		X

SC = Screening; BL = Baseline; C = End of cycle; ESS = Epistaxis severity score; CBC = Complete blood count; CMP = Complete metabolic panel; EOS = End of study Visit; ET = Early termination; QOL = Quality of life; Gray boxes: flexibility to perform visits remotely in which case physical exam may be modified; vital signs and biorepository samples may not be collected.

\* Window to begin study drug dosing cycle (see Section 6.1.5)

 Limited physical examination; \*A detailed physical exam if screening visit was remote.

 Vital signs will include height (only at first in-person visit), body weight, blood pressure, pulse and O2 saturation.

 Genetic testing will be performed only if not done previously or if results for ENG, ACVRL1 and SMAD4 genes are not available and consent is obtained.

 Information on Iron infusion and Blood transfusion over the past 6 months to be collected at screening visit.

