4.5 Study Flow Chart of Assessments and Evaluations

Visit	Screen and Baseline		Treatment Period						End of Study	
	SC	BL	C1	C2	C3	C4	C5	C6	EOS	ET
Study Procedures	Week -4 to -8	Week 0	Week 4 0-5 Days	Week 8 0-5 Days	Week 12 0-5 Days	Week 16 0-5 Days	Week 20 0-5 Days	Week 24 0-5 Days	Week 28 (4 week follow up) 0-7 Days	Only for withdrawn consent
Informed Consent	X									
Enrollment Criteria	X									
Demographics	X									
Medical History	X									
Concomitant Medications	X	X	X	X	X	X	X	X	X	X
Physical Exam	X	X ^{1*}	X ¹	X ¹	X	X ¹	X ¹	X	X	X
Vital Signs ²	X	X	X	X	X	X	X	X	X	X
Genetic Testing ³		X								
Iron Infusion	X ⁴	X	X	X	X	X	X	X	X	X
Blood Transfusion	X ⁴	X	X	X	X	X	X	X	X	X
Adverse Events		X	X	X	X	X	X	X	X	X
ESS	X ⁵	X	X	X	X	X	X	X	X ⁵	X
Epistaxis Duration Diary	X	X ⁶		X	X ⁶		X	X ⁶	X ⁶	
CBC with differential	X	X	X	X	X	X	X	X	X	X
CMP	X	X	X	X	X	X	X	X		X
Iron Studies ⁷	X	X	X	X	X	X	X	X	X	X

Visit	Screen and Baseline		Treatment Period						End of Study	
	SC	BL	C1	C2	C3	C4	C5	C6	EOS	ET
Study Procedures	Week -4 to -8	Week 0	Week 4 0-5 Days	Week 8 0-5 Days	Week 12 0-5 Days	Week 16 0-5 Days	Week 20 0-5 Days	Week 24 0-5 Days	Week 28 (4 week follow up) 0-7 Days	Only for withdrawn consent
INR and aPTT	X									
Biorepository Collection	X ⁸	X ^{8*}			X ⁸			X	X ⁸	X
QOL ⁹ surveys		X			X			X	X	X
Pregnancy Testing ¹⁰	X	X	X	X	X	X	X	X		
Randomization		X								
Drug Dispensation		X	X	X	X	X	X			
Drug Return			X ¹¹	X ¹¹	X	X ¹¹	X ¹¹	X		X

SC = Screening; BL = Baseline; C = End of cycle; ESS = Epistaxis severity score; CBC = Complete blood count; CMP = Complete metabolic panel; EOS = End of study Visit; ET = Early termination; QOL = Quality of life; Gray shaded boxes denote flexibility to perform visits remotely in which case physical exam may be modified; vital signs and biorepository samples may not be collected.

¹ Limited physical examination; *A detailed physical exam if screening visit was remote.

² Vital signs will include body weight, blood pressure, pulse and O₂ saturation.

³ Genetic testing will be performed only if not done previously and consent is obtained.

⁴ Information on Iron infusion and Blood transfusion over the past 6 months to be collected at screening visit.

⁵ ESS will be a 3-month recall for these visits; for all other visits, it will be a 4-week recall.

⁶ Epistaxis Duration Diary will be collected at these visits and if applicable a new diary will be dispensed for the next recording.

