5 ANALYSIS POPULATIONS

Randomization can occur either shortly before or at the baseline visit.

- If the screening visit was completed in-person, randomization can be completed before the baseline visit and study drug is ordered by the site from McKesson (manager of the study drug for Celgene and implementer of the Pomalidomide REMS system) to be shipped to the site so it is available at the site on the day of the baseline visit.
- If the screening visit was completed remotely, then eligibility is confirmed at the baseline visit and randomization occurs at baseline, and the drug is ordered to ship directly to the participant or to the site for dispensing to the participants within a few days of the baseline visit.

Under these scenarios, occasionally a randomized participant might withdraw consent before receiving the study medication from McKesson. Participants might also withdraw consent after receiving study medication but before the first follow-up visit and they may refuse to provide any follow-up assessments. Because these patients have no efficacy data to contribute to the analysis, they are excluded from the efficacy analysis populations, as follows:

Modified Intention-to-Treat Population (mITT)

The modified intention-to-treat population will comprise of all randomized participants who took at least one dose of the double-blind study medication AND have at least one post-baseline efficacy measurement.

Note that if a participant receives study drug sent by McKesson and does not return a full drug bottle to the site, it is assumed that they took at least some study drug.

Participants who receive study drug but do not complete the study will be used in all analyses for which data are available. Participants who withdraw consent for further follow-up will be treated as lost to follow-up at the time that consent was withdrawn, and data will be used up to the time of study withdrawal.

Per-Protocol Population (PP)

The per-protocol population will comprise of all randomized participants who complete the study with no major protocol violations and took at least 80% of the prescribed double-blind medication. Participants who were lost to-follow-up will be considered non-compliant for the purposes of the per-protocol population.

The blinded data review meeting identified the per-protocol exclusions as the following:

- Participants who did not take at least 34 pills of study drug (20%) for reasons other than AEs/side effects,

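### The SAP's recoding of pre-v2.8 early-termination visits uses a 28-day cut-off without the schedule's 0-5 day allowance, so as written a cycle visit due on days 29-33 is filed as post-treatment (EOS)

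*SAP*

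**What the plan says.** The rule is in the outcome modification history of SAP 3.2.4. Its scope is limited: "Prior to the amendment, there were a number of subjects with an early termination (ET) visit" that belonged under a regular study visit or a post-treatment visit. Those cases were reviewed by hand and will be reclassified in all reporting and analysis. The rule has two branches:

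- Cycle branch, when both intervals are short: "number of days since the prior visit and prior study drug dispensing was within 28 days, it was recoded to the next cycle visit".
- EOS branch, when either interval is longer: "days since the prior visit or the prior study drug dispensing was > 28 days, then it was recoded as an EOS visit".

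For the particulars the SAP says only: "Details are documented in the analysis file specification document". That document is not among those supplied.

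Other places bear on the rule:

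- The SAP abbreviation list defines EOS as "End of study visit, scheduled to be 4-weeks post-treatment".
- The SAP 4.5 flow chart gives C1-C6 as the nominal week plus 0-5 days, for example "Week 24 0-5 Days".
- Protocol 6.1.5 lets a new cycle start up to 5 days after the previous 28-day cycle.
- Protocol 7.3.5 has a patient who permanently stops drug mid-cycle complete the visit of that cycle, with EOS 4 weeks after it.
- SAP section 5 says that after remote screening, drug may go to the participant directly or "to the site for dispensing to the participants within a few days of the baseline visit".

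**The concern.** The cycle branch stops at exactly 28 days, while the trial's own calendar allows about 28 to 33 days between cycle assessments. An ET record made when a cycle visit was due, but one to five days after the nominal date, therefore falls into the EOS branch. The rule does not use the date of the last dose.

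The visit clock is also the wrong discriminator. The next cycle visit and EOS are both scheduled about 4 weeks after the visit before them, so days since the prior visit cannot tell them apart. Days since dispensing can. Because the EOS branch joins the two clocks with an *or*, the uninformative clock can override the informative one.

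EOS serves secondary objective 3 (response 4 weeks after stopping) and the exploratory relapse outcome. C1-C6 and EOS all enter the primary MMRM as separate visits (SAP 9.3). A misplaced record would thus put a cycle-visit score into the post-treatment estimate and remove it from the treatment-period visits. If it were due at C6, it would leave the primary contrast. SAP 9.3.1 plans a supportive analysis without the 20 visits held 12 weeks post-treatment, but none for the recoded ET visits.

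**Working it through.** The plan gives no figure for this rule, so the check is on day counts.

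**1. Rule applied to permitted cycle-visit days.** Inputs: the two branches of SAP 3.2.4; 28 days plus 0-5 (SAP 4.5, Protocol 6.1.5); 28 pills per bottle (SAP 8.3); 4-week ESS recall. Take dispensing at the prior visit (day 0) and all 28 pills taken, on days 0-27. On day d the recall covers days d-28 to d-1, so on-drug recall days = 56 - d.

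| Day d | Filed as | On-drug recall days | Share of 28 |
|---|---|---|---|
| 28 | cycle | 28 | 100% |
| 29 | EOS | 27 | 96% |
| 30 | EOS | 26 | 93% |
| 31 | EOS | 25 | 89% |
| 32 | EOS | 24 | 86% |
| 33 | EOS | 23 | 82% |

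Five of the six permitted days go to EOS.

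**2. Cycle 1 with delivery after baseline.** Protocol 7.3.2 has drug shipped overnight after randomization and started on receipt or the next day. Let it arrive, and be started, s days after baseline, with the visit 28 days after arrival. Dispensing clock = 28; visit clock = 28 + s. For s = 1 the visit clock is 29 and the record goes to EOS, although all 28 recall days are on drug. One day of lag is enough.

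**3. True EOS visits.** On the nominal schedule the last dispensing is one cycle before the last cycle visit, and EOS is 28-35 days after that visit. Dispensing clock = 28 + 28 = 56 to 28 + 35 = 63 days. All are filed as EOS, correctly. The error therefore runs one way on the nominal schedule: cycle visits filed as EOS.

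**4. Which clock separates them.** Visit clock: 28-33 days for a cycle visit against 28-35 for EOS, which overlap. Dispensing clock: at most about 33 against at least 56, which do not. On the nominal schedule any dispensing cut-off from 33 to 55 days works. A mid-cycle stopper who follows Protocol 7.3.5 fits the same split, because the current-cycle visit comes first and EOS 4 weeks later.

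**5. Possible size at EOS.** Counts are not given, so this is an assumed range. Shift = share of EOS scores misfiled × on/off-drug difference in treatment effect. Low: 0.02 × 0.5 = 0.01. High: 0.10 × 1.0 = 0.10 ESS points.

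**6. Possible size at week 24.** The plan's t-test figure comes first: 96:48, difference 1.0, SD 1.7, two-sided alpha 0.044. Standard error = 1.7 × √(1/96 + 1/48) = 0.30; power recomputes to 90.1%, against 90% in Protocol 10.5. Removing 2-10 week-24 scores, all from pomalidomide or spread roughly 2:1 over the arms, gives 88.0-89.9%.

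**The case against.** The strongest reply is that the sentence may only summarise a case-by-case review. The SAP says the records were reviewed by hand and points to a specification document that may treat late cycle visits properly. The rule covers only ET records made before v2.8, their number is not stated, and nothing shows that any fell on days 29-33. This stands. A reader might infer that on-treatment scores have already been placed in the post-treatment estimate; the documents do not show that.

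Second, the 28-33 day range is partly inferred. At C1-C5 the protocol's schedule labels the 0-5 days as "Window to begin study drug dosing cycle (see Section 6.1.5"; only C6 lacks that label. The windows in force before v2.8 are not in the documents. This stands as a caution. But Protocol 6.1.5 and the unlabelled SAP flow chart both make such intervals ordinary, and the cycle-1 case in step 2 does not depend on the window.

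Third, ET patients were often stopping drug. The 82-96% figures assume a finished bottle; someone who stopped early in the cycle would be mostly off drug by day 30. This also stands, so these records cannot simply be called on-drug. It does not rescue the rule. Protocol 7.3.5 still makes the visit due at cycle end the current-cycle visit, and a visit 30 days after dispensing is not 4 weeks post-treatment unless drug stopped almost at once, which the rule does not check.

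Fourth, SAP 7.9 promises decisions on out-of-window visits before unmasking. That provision is general, gives no day limits, and does not override an explicit recoding rule.

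Finally, one might infer that misfiling must make the response look more durable. The direction is not established, because early discontinuers may be poor responders.

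**Conclusion.** The written rule conflicts with the visit schedule, with the allowance between cycles in Protocol 6.1.5, and with the order of visits in Protocol 7.3.5. It should be corrected. As worded, it sends a due cycle visit on days 29-33 to EOS, and likewise a cycle-1 visit exactly 28 days after drug that arrived at least one day after baseline. This is a risk created by the rule; misfiling has not been shown.

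A reader might take it as a threat to the primary result. The figures do not support that: even 2-10 lost week-24 scores would cost at most about two percentage points of power (90.1% to 88.0%), and no such loss is documented. The EOS ESS and relapse estimates are more exposed. Even there, the 0.01-0.10 point range rests wholly on assumed shares and differences. It is small beside the 0.30 standard error computed for the week-24 contrast and the minimally important difference of 0.7 in Protocol 10.5. The EOS comparison is not judged for significance (SAP 7.7), and relapse has no test (SAP 9.5).

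**What to change.** Before unmasking, replace the two-clock rule as follows:

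- File an ET record as the next cycle visit if it falls within 33 days (28 + 5) of the last dispensing. Drop days since the prior visit as a criterion.
- Check each record against the last-dose date. Without it, no dispensing cut-off can identify patients who stopped soon after dispensing. The adverse-event window in Protocol 8.3 and the compliance calculation in SAP 8.3 already depend on when drug stopped.
- File as EOS only records that are a post-treatment follow-up in the sense of Protocol 7.3.5.
- Give every remaining record a stated destination, so that none is left unassigned. SAP 7.9 intends all data to be used.
- Report how many ET records were recoded each way, by day count, and how many change under the revised rule.
- Re-run the ESS model with the alternative filing as a sensitivity analysis.

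The cost is a re-check of a short existing list and one SAP sentence, with no new data. If the manual review already treated late cycle visits this way, correcting the sentence and reporting the counts closes the point.
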